5.4 Withdrawal Criteria

- Patients will be discontinued from further study drug administration if any of the following occur:
Intolerable toxicity as determined by the Investigator
- Grade 4 bleeding on either arm of this study
- Development on trial of a deep venous thrombosis, pulmonary embolism or cerebrovascular event on either arm of this study
- Grade ≥ 2 CPK elevation on the EACA arm
- Grade ≥ 3 myalgia on the EACA arm
- Development on trial of disseminated intravascular coagulation (DIC)
- Development on trial of a condition that requires anticoagulation
- A treatment interruption for study-drug (EACA) related non-hematologic toxicities lasting longer than 28 days
- Significant deviation from the protocol or eligibility criteria
- Noncompliance with study or follow-up procedures
- Pregnancy
- Patient withdrawal of consent and decision to discontinue participation
- Termination of the trial
- Any other reason that, in the opinion of the Investigator, would justify removal of the patient from the study

5.5 Study Termination

If the investigator, Data Monitoring Committee, or regulatory agencies discover conditions during the study that indicate that the study or site should be terminated, this action may be taken after appropriate

consultation between the investigator, and Data Monitoring Committee. Conditions that may warrant termination of the study include, but are not limited to:

- The discovery of a serious, unexpected, or unacceptable risk to subjects enrolled in the study
- Submission of knowingly false information from the research facility to the regulatory authorities
- Insufficient adherence to protocol requirements

Study termination and follow-up will be performed in compliance with the conditions set forth in the guidelines for GCP, International Conference on Harmonization of Technical Requirements for Registration of Pharmaceuticals for Human Use.

6. Safety and Quality of Life Assessments

6.1.1 Safety Assessments: Safety will be assessed by routine physical and laboratory evaluations. AEs will be recorded and the severity will be graded according to the NCI CTCAE v.4.0.

6.1.1. Adverse Events: Type, incidence, severity (graded in accordance with the NCI CTCAE v.4.0), timing, seriousness and relatedness, outcome, action taken with study drug, and treatment will be assessed and documented by the investigator continuously throughout the study. Baseline malignancy-related signs and symptoms will be recorded as AEs during the study if they worsen in severity or increase in frequency. Procedures for following AEs at the end of treatment and beyond are outlined in Section 5.1.

6.2. Quality of Life Assessments: Patients will be asked to fill the EQ-5D-5L. The EQ-5D-5L questionnaire is a validated, self-administered general questionnaire of health-related quality of life (HR-QoL) issues, developed by EuroQoL Group. The questionnaire asks patients to rate their HR-QoL for 5 dimensions: mobility, self-care, usual activities, pain/discomfort, and anxiety/depression. The instrument contains a descriptive element, with patients being asked to rate each dimension on a 5-level descriptive severity scale; and a visual analog scale, where the same dimensions are rated along a 100-point visual ruler. Patients for whom a validated translation exists in a language in which they are fluent will complete the EQ-5D-5L during study visits as outlined in the Schedule of Events.

6.3. Study Treatments: Patients will be randomized to receive for bleeding prophylaxis either EACA or prophylactic platelet transfusions. EACA will be self-administered by the patient on a daily schedule.

6.3.1 Dose Selection, Treatment Administration and Compliance

6.3.1.1 EACA

The starting dose of EACA will be 1,000 mg taken orally twice daily. Patients will take the prescribed number of tablets at approximately the same time each day. Patients will be provided a diary card where the date of administration will be recorded. Patients who forget to take their dose more than 6 hours after it is due shall not make up the missed dose. Any missing doses should be recorded, and subsequent training of patients should be documented in the appropriate source record (e.g., clinic chart). The starting dose was selected based on our institutional experience (Section 1.3).

6.3.1.2 Prophylactic Platelet Transfusions

Patients not randomized to the EACA arm with platelet counts $< 20 \times 10^9/L$ in the out-patient or $< 10 \times 10^9/L$ in the in-patient will receive a single donor unit of pheresed platelets in the infusion center after pre-medication with acetaminophen and diphenhydramine per institutional guidelines. Documentation of the transfusion will be maintained according to the hospital's Standard Operating Procedures, with documentation of the start and end time of the infusion, as well as adverse events during the infusion and

its management. Platelet refractory patients will receive prophylactic platelet transfusions as described above.

6.3.1.3 Therapeutic Platelet Transfusions

On both arms of the study, patients will receive therapeutic platelets transfusion for any grade ≥ 2 bleeding per standard of care. Platelet refractory patients will receive HLA match platelet transfusions per standard of care.

6.3.2 Dose Escalation

Patients randomized to EACA who experience any persistent grade ≥ 2 bleeding including hematuria, will receive platelet transfusions as per standard of care and have the option of increasing the dose of EACA to 1,000 mg three times a day. If the dose of 1,000 mg TID is poorly tolerated, then the EACA will be held and restarted at 1,000 mg BID after resolution of the AEs to $<$ grade 1.

If patient experience oral bleeding secondary to acute or chronic gingivitis or mucositis who do not respond to chlorhexidine 0.12% oral rinse and antibiotic treatment (including but not limited to penicillin and metronidazole or amoxicillin and clavulanate or ampicillin and sulbactam or clindamycin), then have the option of increasing the dose of EACA to 1,000 mg three times a day. If the dose of 1,000 mg TID is poorly tolerated, then the EACA will be held and restarted at 1,000 mg BID after resolution of the AEs to $<$ grade 1.

Patients randomized to EACA who have persistent cutaneous bruises will receive platelet transfusions as per standard of care and have the option of increasing the dose of EACA to 1,000 mg three times a day. If the dose of 1,000 mg TID is poorly tolerated, then the EACA will be held and restarted at 1,000 mg BID after resolution of the AEs to $<$ grade 1. If bruising continues, patient will be taken off study.

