- ***Approved indications for the use of EACA:*** EACA is approved by the FDA for treatment of surgical bleeding complications following heart surgery (with or without cardiac bypass procedures) and portacaval shunt; hematological disorders such as megakaryocytic thrombocytopenia (accompanying aplastic anemia); acute and life-threatening abruptio placentae; hepatic cirrhosis; and neoplastic disease such as carcinoma of the prostate, lung, stomach, and cervix. Bleeding associated with surgical hematuria (following prostatectomy and nephrectomy) or nonsurgical hematuria (accompanying polycystic or neoplastic diseases of the genitourinary system secondary to urinary fibrinolysis). Platelet dysfunction and von Willebrand, menorrhagia, gastrointestinal tract bleeding, nose and mouth bleeds and coagulation defects such as hemophilia. In the acute bleeding setting, EACA is administered orally or by IV infusion, at an initial dose of 4-5g during the first hour of treatment, followed by 1-1.25g/hour in order to sustain the plasma concentration of the drug at 130 mcg/ml. Maximum dose recommended is 30 g/24 hours. When the bleeding tendency is chronic in nature, a dosage of 5-30g, for 5 days is generally used although lower daily dosage may also be effective.
- ***Side effects associated with the use of EACA and precautions:*** Table 1 summarizes side effects reported with the use of EACA. Thrombotic complications are rare with the use of EACA, but have been reported in a patient with hemophilia receiving concomitant therapy with factor IX. EACA may accumulate in patient with decreased renal function, and dose-reduction is recommended. EACA is contraindicated in patients with hematuria originating from the upper urinary tract due to intrarenal obstruction via glomerular capillary thrombosis or clots. In patient receiving long term therapy at doses > 10 g/d, elevations of serum creatine kinase concentrations due to skeletal myopathy were reported.
- ***Contraindications for the use of EACA:*** EACA should not be used when there is evidence of an active intravascular clotting process. EACA must not be used in the presence of disseminated intravascular coagulopathy (DIC) without concomitant heparin.
In summary EACA is safe and effective therapy that enhances hemostasis in patients with congenital bleeding disorders and bleeding complicating certain medical conditions and surgical procedures.

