1.4 Rationale for the Conduct of this Study

Given the high incidence of platelet refractoriness, and the prolonged duration of thrombocytopenia in patients with hematological malignancies and marrow failure syndromes, alternatives to platelet transfusions are desperately needed. Our institutional experience with EACA provides a unique expertise to further investigate the role EACA can play in the prevention of bleeding in this patient population. We therefore propose to conduct a prospective, randomized, controlled trial to compare EACA versus standard prophylactic platelet transfusion to prevent bleeding in thrombocytopenic patients with hematological malignancies. The objectives of the trial are to address safety and efficacy of EACA as assessed by major and minor bleeding, cumulative platelet transfusion consumption, quality of life and costs in both arms of the study.

Table 2: Characteristics of 44 thrombocytopenic patients who received epsilon aminocaproic acid for the prevention of bleeding

Age, years median (range)	61 (17-82)
Male/female	29/15
Platelet counts $\times 10^9/L$ when EACA started, median (range)	8 (1 – 19)
Patients with platelet refractoriness n (%)	10 (23%)
Duration of thrombocytopenia in days, median (range)	273 (20-1463)
Diagnosis n (%)	
CML	9 (21)
AML	14 (32)
ALL	1 (2)
MDS	15 (35)
CLL	1 (2)
ITP	1 (2)
Lymphomas	1 (2)
Aplastic anemia	1 (2)
Myelofibrosis	1 (2)
Disease Status of patients at the time EACA started	
Active treatment, n (%)	13 (29)
Relapsed/refractory, n (%)	31 (71)
Duration of EACA therapy, median(range) in days	47 (7-209)
Patients without bleeding on EACA, n (%)	26 (59)
Patients with bleeding episodes while on EACA, n (%)	18 (41)
Patients requiring platelet transfusions for bleeds, n (%)	7 (16%)
Grade and location of the 10 bleeding episodes requiring platelet transfusions:	
Grade 4 – CNS*	1

Grade 3 – rectal	1
Grade 2 – hemorrhoids	1
Grade 2 – hematuria **	2
Grade 2 – epistaxis	1
Grade 2 – oral	3
Grade 2 – vaginal	1
Grade and location of the 19 bleeding episodes not requiring platelet transfusions:	
Grade 1- epistaxis	7
Grade 1 – skin bruises	4
Grade 1 – gingival bleed	2
Grade 1 - vaginal	1
Grade 2 – gingival	2
Grade 2 – vaginal	1
Grade 2 - epistaxis	2
Reason for discontinuing EACA, n (%)	
Death	25 (57)
Increased platelets count	18 (41)
Hematuria	1 (2)

*Traumatic brain injury in a car accident

**One patient had 2 episodes of hematuria

2 Study Objectives and Hypothesis

2.1 Primary Objective:

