6.3.3 Dose Reduction

Patients randomized to EACA 1000 mg twice a day or higher who experience grade ≥ 2 toxicity attributable to EACA, will hold the study drug until resolution of the adverse event to $<$ grade 1. EACA will then be reduced by 50%, restarted at 1000 mg daily after the resolution of the AE's to $<$ grade 1

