11.4 Study Termination

The study will be terminated at any time for any of the following reasons:

- Failure to enroll patients
- Protocol violations
- Inaccurate or incomplete data
- Unsafe or unethical practices
- Questionable safety of the study drug
- Suspected lack of efficacy of the study drug
- Administrative decision

In the event of the termination of the Study, a written statement describing why the study was terminated prematurely will be made available by the investigator

12. References

1. Heddle, NM, A descriptive analysis of international transfusion practice and bleeding outcomes in patients with acute leukemia, *Transfusion* 2006; 46:903-911
2. Gernsheimer, TB Platelet transfusion in the 21st century, *ISBT* 2011;6: 245-248

3. [name]., [name]., [name]., [name]., [name]., [name]., [name]., [name]., and [name]. for the Gruppo Italiano Malattie Ematologiche Maligne dell'Adulto N Engl J Med 1997; 337:1870-187
5. Schiffer, CA et al. Platelet transfusion for patient with cancer, JCO 2001;19:1519
6. Klingemann, H.G Refractoriness to random donor platelet transfusions in patients with aplastic anemia: a multivariate analysis of data from 264 cases. British Journal of 1987 Haematology; 66: 115–121.
7. Legler, T.J Frequency and causes of refractoriness in multiply transfused patients. Annals of Hematology 1997; 74: 185–189.
8. Nevo, S Acute bleeding and thrombocytopenia after bone marrow transplantation. Bone Marrow Transplantation 2001; 27: 65–72.
9. European Medicines Agency. Antifibrinolytic medicine (aminocaproic acid), article 31. 2012.

Appendix 1

WHO grade	Description
0	No bleeding
1	Only petechial bleeding Including retinal bleeding without visual impairment
2	Mild blood loss Including melena, hematuria, hematemesis and hemoptysis
3	Gross blood loss Including any bleeding requiring red cell transfusion
4	Debilitating blood loss Including retinal and cerebral bleeding with high morbidity or fatal outcome

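### Section 6.3.2 offers an optional EACA increase for persistent hematuria without excepting upper-urinary-tract hematuria, which section 1.2.2 calls a contraindication

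*Protocol*

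**What the plan says.** The starting dose is 1,000 mg twice daily (Protocol 6.3.1.1). The first paragraph of 6.3.2 then provides: "Patients randomized to EACA who experience any persistent grade ≥ 2 bleeding including hematuria, will receive platelet transfusions as per standard of care". The same patients "have the option of increasing the dose of EACA to 1,000 mg three times a day". The paragraph names hematuria and does not distinguish its sources.

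Section 1.2.2, in the bullet on side effects and precautions, says: "EACA is contraindicated in patients with hematuria originating from the upper urinary tract due to intrarenal obstruction via glomerular capillary thrombosis or clots". The bullet on approved indications in the same section lists some urinary bleeding as an accepted use: "Bleeding associated with surgical hematuria (following prostatectomy and nephrectomy) or nonsurgical hematuria", the latter when it accompanies polycystic or neoplastic genitourinary disease.

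Appendix 1 describes WHO grade 2 as mild blood loss, "Including melena, hematuria, hematemesis and hemoptysis".

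**The concern.** An investigator treating a patient whose hematuria persists on EACA will turn to the dosing section. There, hematuria is named as a ground for giving more drug. The warning that one kind of hematuria is a contraindication stands in the background section, and 6.3.2 does not refer to it. Within the dosing text, a patient with known or suspected upper-tract bleeding may stay on EACA and move to a higher dose. The harm at stake is the one section 1.2.2 names, obstruction within the kidney. Section 1.2.2 also warns that EACA may accumulate when renal function falls, so a higher dose would be harder to justify if obstruction had begun.

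**Working it through.** **1. Does hematuria meet the trigger?** Yes on grade. Appendix 1 places hematuria in WHO grade 2, and 6.3.2 starts at grade 2. Persistence and the investigator's choice are the only remaining conditions.

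**2. Does another section supply the exception?**

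| Section | What it does | Covers upper-tract hematuria arising on treatment? |
|---|---|---|
| 4.2 | Excludes active bleeding of grade 2 or higher, hematuria included | No; applies at randomization only |
| 5.4 | Lists study-drug stops: "Patients will be discontinued from further study drug administration if any of the following occur" | Not listed; grade 4 is the only bleeding stop. Two discretionary grounds remain: intolerable toxicity as judged by the investigator, and a general other-reason clause |
| 6.3.3 | Grade 2 or higher "toxicity attributable to EACA, will hold the study drug until resolution of the adverse event" | Only if the event is attributed to EACA; hematuria in a severely thrombocytopenic patient is more readily read as bleeding |
| 6.3.2, third paragraph | Takes patients off study if bruising continues | No; bruising only |
| 6.5.2 | Prohibits certain medications in patients on EACA | No |

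Other hazards in 1.2.2 do have operating rules. Thrombosis, DIC, CPK elevation and myalgia are stops in 5.4, and renal dysfunction is an exclusion in 4.2. Upper-tract hematuria has no on-treatment rule.

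**3. Size of the dose step.**
- Start: 2 × 1,000 = 2,000 mg/day (6.3.1.1).
- Escalated: 3 × 1,000 = 3,000 mg/day (6.3.2).
- Change: 3,000 / 2,000 − 1 = +50%.
- Context: section 1.2.2 gives a maximum of 30 g per 24 hours, and 3 / 30 = 10% of it.

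**4. How often hematuria might arise.** Table 2 lists two grade 2 hematuria episodes, with the footnote "One patient had 2 episodes of hematuria", so 1 of 44 patients was affected.
- Proportion: 1/44 = 0.0227, or 2.3%.
- Exact (Clopper-Pearson) lower limit: 1 − 0.975^(1/44) = 0.000575, or 0.06%.
- Upper limit: the p that solves (1−p)^44 + 44p(1−p)^43 = 0.025, which is 0.1202, or 12.0%.
- Applied to 50 EACA patients: 50 × 0.0227 = 1.14 expected, with limits 50 × 0.000575 = 0.03 and 50 × 0.1202 = 6.0.

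These figures are for hematuria from any source. The upper-tract share and the persistence of the pilot bleeds are not reported. Pilot exposure was a median of 47 days, against up to 6 months here. The result is an order of magnitude. The upper limit is a confidence limit on an expected count and does not cap the number of patients.

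**The case against.** Several points on the other side have force.

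- **Escalation is optional, and the warning is in the same protocol.** A reader might infer that 6.3.2 tells investigators to give a contraindicated dose. It does not: the two sections collide only if the investigator chooses to escalate. What stands against the text is narrower. It names hematuria as a ground for escalation and leaves out the exception that the same document calls for.
- **Other safeguards exist.** Section 5.4 has two discretionary grounds, Table 1 lists renal failure and kidney disorders among the risks of EACA, and the metabolic panel at scheduled visits includes creatinine and urea nitrogen. Renal injury of grade 2 or higher attributed to EACA would trigger the hold in 6.3.3. This is right, but the attribution-based hold acts after harm begins, and 5.4 relies on judgement.
- **Pilot practice was to stop.** Table 2 gives hematuria as the reason for discontinuing EACA in 1 patient (2%). It does not say whether this was the patient with the two episodes, nor where the bleeding arose. It makes it less likely that such patients would in practice be escalated. It also shows that the written rule departs from what was once done.
- **Some urinary bleeding is an approved use.** Bleeding after nephrectomy or with polycystic disease can arise in the upper tract. A reader might infer that confirmed upper-tract hematuria should be a permanent stop in 5.4. The documents do not support that. It would bar uses that 1.2.2 lists as approved, and it would depend on locating the source, for which the schedule in Table 3 has no urinalysis or imaging.
- **The dose stays low.** At 10% of the stated daily maximum, the 50% step is modest. The contraindication applies at 2,000 mg/day as well, which is why the remedy needs to address holding the drug in addition to the increase.

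**Conclusion.** The point holds in a limited form. Section 6.3.2 permits an optional 50% increase in EACA for persistent hematuria of any source, while section 1.2.2 calls EACA contraindicated when the source is the upper urinary tract. The rest of the protocol either leaves that case to the investigator's discretion or acts only on toxicity attributed to EACA. Because 1.2.2 points both ways on urinary bleeding, the boundary should be written into the dosing rule.

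The size is small: about 1 of 50 EACA patients on the pilot rate for hematuria of any origin, with a wide interval and an unknown upper-tract share. That estimate assumes the pilot rate carries over to this trial despite longer exposure. The conflict itself does not depend on the estimate. This is a minor patient-safety correction, and no effect on the primary analysis is claimed.

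**What to change.** In the first paragraph of 6.3.2, directly after the mention of hematuria, add:

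*except hematuria that the investigator knows or suspects to be of upper-urinary-tract origin, for which EACA must not be escalated and should be held (see 1.2.2) unless the investigator documents that it falls under a use listed as approved in 1.2.2; therapeutic platelets are given per 6.3.1.3 and bleeding follow-up continues for the ITT analysis*

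All other hematuria stays under the present rule. No new stop in 5.4 and no new test are needed, since the clause acts on what the investigator knows or suspects.

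The text cost is one clause. The clinical cost is that a small number of EACA patients would have the drug held. Meanwhile they would have therapeutic platelets but no prophylaxis. This matters most in platelet-refractory patients (10 of 44 in the pilot, 23%), who would receive HLA-matched units under 6.3.1.3.

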The primary objective of this study is to compare the proportion of patients who develop major bleeding episodes (WHO grades 3-4) in the group randomized to receive prophylactic EACA versus standard of care prophylactic platelet transfusions.

2.2 Secondary Objectives:

- To compare the proportion of patients who develop any bleeding episode in the group randomized to receive prophylactic EACA versus standard of care prophylactic platelet transfusions.
- To compare, according to treatment with prophylactic EACA or prophylactic platelet transfusions, the total number of units of platelet transfused
- To compare the quality of life in both arms of the study

2.3 Hypothesis:

This is a non-inferiority trial in which we hypothesize that in thrombocytopenic patients with hematological malignancies, comparable incidence of bleeding will be observed with the prophylactic use of EACA and standard of care arm prophylactic platelet transfusions.

3 Investigational Plan

3.1 Overall Study Design and Plan:

This is a single center, randomized phase 2, open label trial of oral EACA versus platelet transfusions for the prevention of bleeding in thrombocytopenic patients with hematological malignancies.

Eligible patients with acute or chronic thrombocytopenia will be randomized in a 1:1 fashion to receive oral EACA at the dose of 1,000 mg twice daily as a substitute for prophylactic platelet transfusions or standard of care prophylactic platelet transfusions for an untransfused platelet count $< 20 \times 10^9/L$ in the out-patient or in the in-patient setting. Patients will be assessed twice weekly and as needed in between visits for the presence of bleeding. The number of platelets transfused for prophylaxis (arm B) or for therapeutic purposes (both arms) will be monitored. Patients will complete quality of life questionnaire. Adverse events will be assessed and graded according to the National Cancer Institute Common Terminology Criteria for Adverse Events (CTCAE) version 4.0. Bleeding will be assessed and graded according to the World Health Organization (WHO) classification [Appendix 1]. Patients will be assessed according to a protocol-specific schedule of events. Patients will continue treatment on trial until one or more criteria for discontinuation are met. Patients will be supplied with study drug until they discontinue from the study. Patients will be followed for 2 years or death, whichever occurs first.

3.2. Primary Endpoint:

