Bleeding score: Bleeding will be graded according with the WHO bleeding scale (Appendix 1) and recorded in the medical records during each visit. For hospitalized subjects enrolled on this trial, bleeding will be described in the daily follow up note by physician, nurse practitioner or physician assistant and graded by the investigator.

End of Treatment or Early Termination Procedures: The End-of-Treatment (or early termination) Visit should be performed within 2 weeks (14 days) of the patient's last dose of study drug or the patient/investigator decision to end treatment, whichever is later.

Follow-up Procedures: Safety: All AEs ongoing or starting within 30 days after the End-of-Treatment must be recorded on the CRF. After this time, ongoing AEs thought to be at least possibly study-drug related and all ongoing SAEs should be followed at least every 4 weeks until they resolve to baseline (or CTCAE grade ≤ 1), stabilize, or are considered to be chronic or irreversible.

Follow-up Procedures: Survival: Survival data will be collected every 12 weeks \pm 2 weeks starting after the last dose of the assigned study treatment or the investigator/patient decision to discontinue treatment, whichever occurs later and continuing for up to 12 months from the time the last patient is randomized to a treatment group. These data do not need to be obtained during a visit; phone contact is acceptable.

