5.2.2 Early Discontinuation

In the event that a patient is withdrawn from the study, every effort will be made by the Investigator to document and report the reasons for withdrawal as thoroughly as possible. The reason(s) for termination must be clearly reported on the appropriate page of the patient's CRF. An End-of-Treatment reason for discontinuation must be recorded for any patient who is randomized. If a patient is discontinued from the trial for any reason, every effort must be made to perform all clinical and laboratory procedures as scheduled for the End-of-Treatment Visit. In the event that the patient fails to return for the necessary visit(s), an effort must be made to contact the patient to determine the reason, and this information should be recorded in the appropriate source record and the end-of-treatment CRF.

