5.3 Study Duration and End of Treatment

The total estimated duration of the study is up to 3 year, including 14 months to accrue patients with up to 1 year for treatment and follow up for the last patient. Patients will be supplied study drug until they discontinue from the study.

End of treatment is defined when untransfused platelet count recover to $> 30 \times 10^9/L$ on 2 measurements obtained 5 days apart. For patients without platelets recovery, end of treatment will be set at 6 months. At that time patients will be taken off treatment and enter a long-term follow-up period for 2 years.

Subjects that completed treatment due to platelet count recover to $> 30 \times 10^9/L$ on 2 measurements obtained 5 days apart whom developed thrombocytopenia > 30 days of end of study and fulfill the inclusions and exclusion criteria are allowed to be re-enrolled in the study. Subjects without platelet recovery that completed 6 months of treatment are not allowed to be re-enrolled in the study

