8.5.2 Primary Endpoint Analysis

The primary analysis of the primary endpoint will be performed using a one-sided fisher exact test to compare the proportions of patients with major bleeding during the whole study between the two arms. The significance level is set at 0.05. This primary analysis will be based on the ITT population.

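### Section 6.3.2 takes only EACA patients off study for continuing bruising, and no WHO bleeding assessment is required after their exit visit, although major bleeding is compared over the whole study in all randomized patients

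*Protocol*

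**What the plan says.** - **Exit rule.** Section 6.3.2, in its paragraph on patients randomized to EACA who have persistent bruises, ends: "If bruising continues, patient will be taken off study". Section 5.4 does not list bruising. Its last item, at the investigator's discretion, can remove a patient from either arm.
- **Primary analysis.** Section 8.5.2 uses a one-sided Fisher exact test to "compare the proportions of patients with major bleeding during the whole study between the two arms", in the ITT population. Section 8.2 defines that as everyone randomized.
- **After an exit.** Section 5.2.2 asks for every effort to "perform all clinical and laboratory procedures as scheduled for the End-of-Treatment Visit". Table 3 includes a WHO score at that visit. Section 5.1 places the visit within 14 days of the "last dose of study drug or the patient/investigator decision to end treatment, whichever is later". Then "All AEs ongoing or starting within 30 days after the End-of-Treatment must be recorded on the CRF", and AEs are graded by CTCAE (6.1.1). Beyond that, 5.1 describes follow-up of ongoing related AEs and SAEs, and survival contact.
- **Long-term follow-up.** Section 3.1 adds: "Patients will be followed for 2 years or death, whichever occurs first". Section 5.3 also mentions two years. Neither states any bleeding assessment.
- **Patients who stay.** Section 5.3 says: "For patients without platelets recovery, end of treatment will be set at 6 months". Until then Table 3 has monthly visits with a WHO score. Its footnote says that after 30 days the score follows standard of care for cytopenic patients.

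**The concern.** An intention-to-treat comparison over the whole study needs the endpoint to be sought over the same period in everyone randomized. The bruising rule works against this in one arm, and its trigger is related to the outcome, since skin bruises are graded as bleeding (grade 1) in Table 2. The decision is made open label. An EACA patient removed early can have a grade 3-4 bleed months later that nobody was asked to look for or grade by WHO. A platelet-arm patient without platelet recovery is still on the Table 3 schedule.

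If the removed patient is then counted as a non-bleeder, the lost event lowers the observed EACA rate and moves a one-sided test towards EACA. The 10% dropout allowance in 8.4 adds patients, but it does not correct loss that occurs in one arm for a bleeding-related reason. An analysis plan cannot repair this later, because it cannot analyse bleeds that the protocol did not require anyone to collect.

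**Working it through.** **The plan's own figure.** Exact power of the one-sided Fisher test at 8% versus 30%, 45 per arm, level 0.05, is 80.05% (stated: 80%). 45/(1 - 0.10) = 50 per arm. Both reproduce, so the sample size is not in question.

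**Inputs from the protocol**
- 50 per arm, one-sided level 0.05, 30% major bleeding with platelets (8.4).
- W = 168 days: six 28-day months (5.3 and 8.1). Alternative W = 47 days: median EACA duration in Table 2.
- c = 30 days of AE capture after exit (5.1), assuming that such bleeds are then counted as endpoints. Alternative c = 14 + 30 = 44 days if the exit visit falls at the end of its window.
- Bruising exits: Table 2 has 0 of 44 stopping EACA for bruising (exact 95% upper limit 8.0%). It has 4 bruise episodes; read as four patients who all left, 4/44 = 9.1% (95% CI 2.5-21.7%).

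**Assumptions**
- True risk is 30% in both arms (the null case).
- A fraction r of EACA patients leave at fraction u of W.
- Their bleeding hazard is k times that of the others.
- Bleeds after the capture period are lost, and the patient counts as a non-bleeder.

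**Formulas**
- Solve for λ: (1 - r)(1 - exp(-λW)) + r(1 - exp(-kλW)) = 0.30.
- Missed proportion: m = r[exp(-kλ(uW + c)) - exp(-kλW)], and zero if uW + c ≥ W.
- Error = exact probability that Fisher's test favours EACA when the observed risks are 0.30 - m and 0.30.

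**Worked case.** r = 0.08, k = 2, u = 0.25, W = 168, c = 30:
- λ = 0.001986 per day, and uW + c = 42 + 30 = 72 days.
- m = 0.08 × (0.7512 - 0.5130) = 0.0191.
- Observed EACA risk = 0.2809, giving an error of 4.9%.

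**Results.** With no loss the error is 3.2%. Each range runs over (k, u) = (1, 0.5), (2, 0.5), (2, 0.25).

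| Window and capture | r = 2% | r = 8% | r = 9.1% |
|---|---|---|---|
| 47 days, 30-day capture | 3.2-3.2% | 3.2-3.4% | 3.2-3.5% |
| 168 days, 30-day capture | 3.3-3.6% | 3.7-4.9% | 3.8-5.2% |
| 168 days, 44-day capture | 3.3-3.5% | 3.6-4.6% | 3.6-4.8% |
| 168 days, 30-day capture, half of later bleeds found in charts | 3.2-3.4% | 3.4-4.0% | 3.5-4.1% |
| 168 days, no later capture | 3.4-3.7% | 4.1-5.8% | 4.2-6.2% |

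Over 168 days with 30-day capture, the expected number of missed bleeds is 50m = 0.09 (r = 2%, k = 1, u = 0.5) to 1.08 (r = 9.1%, k = 2, u = 0.25), out of 50 × 0.30 = 15 true EACA major bleeds. At the final level of 0.043 (8.8), the error is 2.7% with no loss and 2.8-4.3% at 2-8% exits with 30-day capture. The figures treat the test as a single look.

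**The case against.** The case against is strong on size and on several details.

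- **Outcome collection does not stop at exit.** A WHO score is due at the End-of-Treatment visit, AEs run for 30 more days, and a bleed that leads to admission in that period is an SAE. This stands. A reader might infer that nothing about bleeding is recorded after removal, and the documents do not support that. The gap begins after the exit visit for WHO grading and after the 30 days for new events.
- **Removal is not exclusive to EACA.** This also stands, because the discretionary item in 5.4 covers both arms. Only the explicit bruising rule is one-sided.
- **Late scoring rests on standard of care in both arms.** This is correct and narrows the contrast. The platelet-arm patient still has monthly visits with a WHO score in Table 3; the removed patient has none.
- **The direction depends on how removed patients are counted.** The protocol does not say, and an analysis plan may. The bias towards EACA is therefore conditional.
- **The numbers are generous.** No one in Table 2 stopped for bruising, and 43 of 44 stopped for death or a raised platelet count. The 9.1% figure treats every bruise episode as a separate removal. At 47 days with 44-day capture the error does not move from 3.2%.
- **Charts could recover some events.** Grade 3 includes any bleeding that needs red cell transfusion, and there is one centre. This is plausible, but nothing requires the search or the WHO grade.

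A reader might also extend the point to the EACA-only stops in 5.4 (CPK, myalgia, long interruption). The text there is ambiguous, not clearly deficient. Section 5.4 says "Patients will be discontinued from further study drug administration if any of the following occur", which concerns the drug and not the study. Section 5.1 ties the End-of-Treatment visit to the last dose or the decision to end treatment, while 5.3 defines end of treatment as platelet recovery or 6 months. Whether scoring continues depends on which section is followed.

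**Conclusion.** The point holds as a modest, correctable weakness. Following the text of 6.3.2 can end WHO bleeding assessment early in the EACA arm on a bleeding-related trigger, while 8.5.2 counts those patients over the whole study.

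The size is probably small: an error of 3.2-3.4% over 47 days and 3.3-4.9% over 168 days, against 3.2% with no loss. This rests on an assumed 2-8% exit rate, an assumed 30% risk in both arms, and removed patients counted as non-bleeders. The exit rate and later risk are not given in the protocol, and the Table 2 cohort was not managed under these rules.

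A reader might infer that the trial's error rate is inflated beyond 5%. The protocol's figures do not support that. In this model it happens only when high exits (8% or more), early exit and doubled hazard coincide: 5.2% at 9.1% exits with 30-day capture, and 5.8-6.2% at 8-9.1% exits if the prescribed AE capture is ignored. A cruder calculation gives 5.9-12.2%. It assumes that 9% of EACA patients are removed, that 30-70% of them bleed later, and that every such bleed is lost, so it too ignores the AE capture. The case for acting is the low cost of the remedy, not the size of the bias.

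**What to change.** Leave every treatment-stopping rule as it is.

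1. In 6.3.2, 5.4 and 5.2.2, state that stopping study treatment is not leaving the study.
2. State that, unless consent is withdrawn, WHO grade 3-4 bleeding ascertainment continues by visit, phone or chart review on the same schedule in both arms, to the end point in 5.3 (platelet recovery or 6 months).
3. In 8.5.2, count these bleeds by assigned arm.
4. Reconcile the timing of the End-of-Treatment visit in 5.1 with the definition of end of treatment in 5.3.

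The cost is one clarifying amendment and monthly phone or chart checks for about 1 to 5 of 50 EACA patients (0.02 × 50 = 1; 0.091 × 50 = 4.6) at one centre. The Table 3 footnote already accepts bleeding scores by phone. The downside is light extra follow-up, and bleeds after EACA stops slightly dilute the treatment contrast.
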